Healthcare Utilization and Direct and Indirect Costs: [*We will collect both direct and indirect costs due to lost work productivity related to LBP over the 1-year follow-up.*] We will use a cost diary method integrated into the web-based data collection system to collect utilization and cost data. Cost diaries offer advantages in terms of feasibility and validity as compared with patient-reported questionnaires for collecting cost data and provide information at regular intervals instead of relying on patient recall over a long time period, minimizing recall error.¹⁰⁹ [*We will collect cost and utilization data monthly via REDCap using the input options outlined below.*] The cost diary will be modeled on paper-based methods with high compliance (85%) for economic analysis in studies of patients with LBP.^{108,131} This compliance rate is consistent with our experience using this method in our ongoing study. Prior research reports no differences between cost

diaries completed for an entire year and extrapolation of data for limited time periods, indicating a robustness to impute scores for random missing data. Patient-reported cost diary data has been found to generally agree with insurance claims, supporting the validity of the self-report cost and utilization data.¹⁰⁸ [*Each monthly cost diary will ask patients if they have utilized healthcare resources in the past month specifically for LBP in 4 categories: 1) provider visits (traditional or complementary/alternative), 2) medications (prescription or over-the-counter), 3) interventions (injections, surgery, etc.), or testing (x-rays, MRI, etc.), and 4) lost time from work or decreased work productivity. Conditional logic will be used to reduce response burden for patients not seeking any care. Patients who are seeking care will be given follow-up questions to ascertain the number and nature of utilization in each category in the past month.]*

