Once a patient is enrolled, the Study Coordinator will create a patient profile in REDCap and the patient will receive a unique ID generated prior to beginning the study. The patient profile will be identified by the unique ID and will not contain any Personal Health Information in REDCap. Links between the ID and patients' identifying information will be maintained by the PI and will be available only to the Study Coordinator. After a patient profile is created the patient and investigators are able to input data directly into REDCap. Once data collection begins, the PI will be in at least weekly communication with the Study Coordinator to monitor overall progress, recruitment and identify any issues that could impact the safety or ethics of the study (e.g, adverse events, instances of unblinding, etc.).

C.9 Data Analysis

Data analyses will be carried out by the SDBC directed by [name], who has extensive experience as a data coordinating statistician for clinical trials with recognized expertise in longitudinal data analysis. The SDBC employs biostatisticians with broad expertise, including [name], who will carry out project analyses directed by [name]. The SDBC will internally review data distributions for extreme scores or inconsistent results and will notify the PI of problematic data. Because data quality and completeness will be monitored throughout, we expect any data discrepancies to be resolved and the study database closed within weeks of completing data collection. Following database closure the SDBC will provide data summaries with descriptive statistics including central tendency and dispersion computed for continuous data and frequency distributions for categorical data. Transformations will be sought for variables failing to meet distribution assumptions. We are aware that unadjusted between-group comparisons are valid if randomization is achieved, however pre-treatment characteristics of the groups will be compared to assess for chance imbalances. If differences are found these variables may be used as covariates in post-hoc sensitivity analyses. Intention-to-treat principles will be used with all patients analyzed in their randomized group regardless of compliance. We will compare compliance between groups and "per-protocol" secondary analyses may be considered if non-compliance is high or disproportionate between groups.

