Multiple imputation (MI) will be used to address missing outcome data. MI incorporates baseline and followup factors beyond the variable being analyzed into imputation models to account for dependence of missing data on other factors. We will use the Markov Chain Monte Carlo method to generate imputed values¹¹⁶ involving 4 steps: 1) preparing the dataset by identifying all outcome variables likely to be involved in later analyses and likely predictors of missingness, evaluating distributional assumptions with transformations as needed; 2) conducting the MI, with variance and covariance estimates based on observed data used to iteratively estimate maximum likelihood values for all subjects. Multiple replacement values for each missing score are drawn randomly from the posterior distribution and perturbed with error; 3) analyses are done identically on all versions of imputed data; and 4) parameter estimates and tests are combined and adjusted for between-imputation variance to yield final results. MI is valid if data are missing at random, meaning the probability of missingness is independent of the missing outcome values after accounting for predictor variables in the imputation model. Moderate violations of this assumption do not substantially bias MI results if the proportion of patients with missing data is low. We will evaluate the assumption with importance sampling to evaluate implications of violations of the missing at random assumption after completion of the basic MI procedure.¹¹⁷ If this approach suggests strong dependence of the results on the missing at random assumption further sensitivity analyses will be performed using formal pattern mixture models.¹¹⁸ Should sensitivity analyses indicate strong dependence of our results on untestable assumptions about missing data, this limitation to the interpretation of our results will be noted and conclusions appropriately qualified. Because this study involves procedures with minimal risk we will not plan interim analyzes to avoid inflating type I error rates. Treatment comparisons will be performed separately at each follow-up time to characterize treatment effects at critical junctures over the follow-up. The 4-week assessment will evaluate effects at completion of treatment; 6 month and 1 year assessments will evaluate intermediate and longterm effects respectively. We now lay out the analysis for each Specific Aim.

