[We will use parametric and non-parametric methods to compare costs between treatments. As the mean is the most useful statistic to evaluate costs related to treatment implementation,¹³⁴ we will calculate means and standard deviations for direct, indirect and total cost by group. We will explore cost data distributions graphically and statistically. With univariate and multivariate techniques we will examine the relationship between treatment and total cost. As cost data are typically skewed we will use nonparametric bootstrapping methods with 2000 pair-wise replications to compare mean costs and avoid distributional assumptions.¹³⁵ Confidence intervals around the mean cost difference will be calculated with bias corrected and accelerated methods.¹³⁶ Regression analyses will also be used to allow costs to be adjusted for patient factors such as socioeconomic status or co-morbidities. We will perform separate analyses for patients with complete cost data and those with imputed costs. Missing cost data will be handled using MI as described.¹³⁷ MI is preferred for missing cost data over alternatives such as last score forward or mean imputation.¹³⁹ Shortand long-term cost-effectiveness (CE) analyses will be conducted. The short-term analysis will use direct and indirect costs over the first 4 weeks. The effectiveness of these costs will be based on OSW and EQ-5D scores at 4 weeks. Long-term CE analysis will use cost and effect data measured at 1-year. Costs and effects will be measured in the same year; eliminating the need for inflation adjustment or discounts. Once 3 parameters are computed: 1) mean differences in cost and effect between treatments, 2) variances for differences in costs and effects, and 3) covariance between effectiveness and cost difference, the incremental cost-effectiveness ratio or incremental net benefits summarizing the monetary value of the intervention will be calculated.¹⁴⁰ A CE acceptability curve will be used to quantify and graphically depict uncertainty in the analysis.¹⁴² To consider uncertainty in parameters, probabilistic sensitivity analysis will be conducted. To reflect the uncertainties in costs and in effects, a gamma distribution will be adopted.]

Specific Aim #3: "Evaluate moderators of improvement with early physical therapy."

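### Missing costs are sent to a covariance-based MCMC imputation with open-ended transformations, which suits zero-heavy costs poorly and can bias mean cost

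*Protocol*

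**What the plan says.** Protocol C.9, Specific Aim #2, disposes of incomplete costs in one sentence: "Missing cost data will be handled using MI as described". The general part of C.9 holds the only description it can mean: "We will use the Markov Chain Monte Carlo method to generate imputed values". The data are prepared by "evaluating distributional assumptions with transformations as needed", and imputation then proceeds "with variance and covariance estimates based on observed data used to iteratively estimate maximum likelihood values for all subjects". C.9 adds a general rule: "Transformations will be sought for variables failing to meet distribution assumptions".

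On the data themselves, C.5 says "We will collect cost and utilization data monthly via REDCap using the input options outlined below" and "Conditional logic will be used to reduce response burden for patients not seeking any care". The Aim #2 text calls costs skewed, takes the mean as the most useful summary, and bootstraps with 2000 replications "to compare mean costs and avoid distributional assumptions". It also plans separate analyses of patients with complete and with imputed costs. The gamma distribution it mentions is for the probabilistic sensitivity analysis, not for imputation.

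SAP section 2 describes sequential imputation with 25 data sets for the primary and secondary numeric outcomes. Costs are not among its variables, and the SAP contains no cost analysis.

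**The concern.** A method that works from means and covariances, checks distributions and transforms where they fail is, in practice, a multivariate normal model, although the Protocol does not use that word. A variable with a spike at zero and a long right tail cannot be transformed to normality. Two things can go wrong. On the raw scale the model draws impossible negative costs. On a log scale it places draws between the spike and the tail, or out beyond the tail, and back-transformation turns these into a wrong mean.

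The documents support many zeros without counting them. The diary has a branch for patients who seek no care. SAP section 3 says the major utilization events generally came early in follow-up. SAP section 4 models monthly missed work as a negative binomial count, with a separate any/none analysis.

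At stake are mean cost per arm, the cost difference, net benefit and the acceptability curve. The plan bootstraps to avoid a distributional assumption, but the imputation step before it brings one back.

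**Working it through.** **Inputs.** The documents give no share of zero months, cost variance or expected amount of missing cost data. The one usable figure is the 85% compliance reported for paper diaries (C.5), read here as 15% of monthly diaries missing. Everything else is assumed: 50%, 70% or 85% zero months; lognormal non-zero months with log-SD 1.0 to 1.5 and mean 300 or 2000; 220 patients, 12 months.

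**Step 1: raw scale, by hand.** Let q be the share of non-zero months, m their mean, s the log-SD (1.2). Then mean = q·m and variance = q·m²·exp(s²) − (q·m)². For q = 0.5, m = 300: mean 150, variance 0.5 × 90,000 × 4.22 − 22,500 ≈ 167,400, SD 409. A normal draw is negative with probability Φ(−150/409) = 0.357. Simulation gave 0.355. The mean of the draws is still 150, so mean cost is unbiased. If negatives are set to zero, the mean draw is 150·Φ(0.367) + 409·φ(0.367) ≈ 249, or 1.66 times the truth. With 15% imputed, the overall ratio is 0.85 + 0.15 × 1.66 = 1.10.

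**Step 2: log(x+1), by hand.** For non-zero months, mean log cost L ≈ ln(m) − s²/2. On the log scale the mean is q·L and the variance is q(1−q)L² + q·s². The back-transformed mean is exp(mean + variance/2) − 1.

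- q = 0.5, m = 2000: L = 6.88, mean 3.44, variance 11.84 + 0.72 = 12.56. Back-transformed: exp(9.72) ≈ 16,600 against a true 1,000. Overall ratio 0.85 + 0.15 × 16.6 = 3.3 (simulated 4.2).
- q = 0.15, m = 300: L = 4.98, mean 0.75, variance 3.17 + 0.22 = 3.38. Back-transformed: about 10.5 against a true 45. Overall ratio 0.85 + 0.15 × 0.23 = 0.89 (simulated 0.94).

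The same transformation can therefore inflate or deflate. These hand figures ignore the other months as predictors, so they approximate the simulated ones.

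**Step 3: square root.** If normal draws match the mean and variance of √cost, the mean of their squares is mean² + variance, which is the mean of cost itself. Little bias is expected.

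**Step 4: simulation, diaries missing completely at random** (4 or 5 data sets per scenario, so approximate):

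| Scale used for imputation | Imputed / true mean annual cost |
|---|---|
| Raw (32–44% of imputed months negative) | 0.99–1.02 |
| Raw, negatives set to zero | 1.08–1.23 |
| log(x+0.01) | about 1.7–112 |
| log(x+1), non-zero mean 300 | 0.91–1.43 |
| log(x+1), non-zero mean 2000 | 0.95–4.2 |
| log(x+10) | 0.92–1.18 |
| log(x+100) | 0.93–1.00 |
| Square root | 1.00–1.03 |

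Imputing annual totals does not remove the problem. On the raw scale 21–31% of imputed totals were negative, with the mean ratio about 1.00. With log(x+1) the median ratio was 1.2–1.4 and the mean ratio 1.6–3.2.

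**Step 5: simulation, missingness related to severity** (64% zero months, 15% missing). Raw 1.01 with 36% negative; truncated 1.11; log(x+1) 1.40 (median 1.28); square root 0.99; log(x+100) 0.96; predictive mean matching 1.00. Patients with complete diaries alone: 0.57.

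**Step 6: difference between arms.** With equal true costs (about $905 a year), and 20% (UC) against 10% (EPT) of diaries assumed missing, the false difference was about $270 (median) with log(x+1), $46 with truncation and −$7 with matching. In a smaller check of 14 replicates, raw, square root and log(x+100) gave −$11, +$9 and −$21 (standard errors $18–30), none distinguishable from zero.

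**Step 7: patients left for the complete-data analysis.** If monthly misses are independent, 0.85¹² = 0.142, about 31 of 220. If they fall entirely in the same patients, the figure is 0.85 × 220 = 187.

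**The case against.** The strongest reply is that the plan commits to none of the harmful choices. It names no log, no added constant, no truncation and no level of imputation, and it never says normal. Negative draws leave the mean, which is the plan's target, almost untouched. A square root would do little harm. Zeros may be fewer than assumed, since the diaries also count over-the-counter medication and reduced performance at work. The plan will inspect cost distributions, and gross inflation would probably show against the complete-data analysis. The sentence on missing costs also carries citations whose content cannot be seen here.

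Most of this stands as a limit on the claim. A reader might infer that the method must yield negative costs or inflated means, but the documents do not support that: the outcome turns on choices they leave open. Nor do they support expecting a false cost difference, because nothing suggests that diary completion will differ by arm. It would also go too far to say that the SAP confirms MCMC for costs, because it neither confirms nor revises the cost method.

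What does not stand is the comfort taken from the complete-data analysis. It may retain few patients, and when missingness follows severity it is itself badly biased (0.57 in Step 5). It could not show which figure is wrong.

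**Conclusion.** The point holds as a poorly suited method with a consequential choice left open, not as a certain error. Following the plan in a common way, by log-transforming skewed costs, imputing and back-transforming, can move mean cost from about 9% too low to about four times too high with log(x+1), and further with a smaller added constant. Leaving costs untransformed keeps the mean within about 2% but produces impossible values, and correcting those by truncation adds 8% to 23%. A square root or a large constant largely avoids the bias, so a ban on every transformed-normal model is not justified.

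These sizes rest on assumed cost levels, zero shares and log-SDs, on reading 85% compliance as 15% of diaries missing, and on few replicates. They show how sensitive the result is; they do not predict this trial's error. The point should be acted on, but it concerns only the Aim 2 cost and cost-effectiveness results. The 6-month OSW comparison is untouched.

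**What to change.** In Protocol C.9, Specific Aim #2, replace the cross-reference with a stated cost-imputation model:

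- Impute missing monthly costs, either as a total or as direct and indirect costs, separately by arm. Use chained equations with predictive mean matching, or a two-part model (any cost, then amount).
- Use as predictors the other months' costs, baseline OSW and NPRS, and observed follow-up OSW and EQ-5D.
- Do not back-transform log-normal draws, and do not set negative draws to zero.
- State how the imputations are combined with the 2000 bootstrap replications and the bias-corrected and accelerated interval. Re-imputing within each replicate is one option, not the only one.
- Keep the complete-data analysis as a description, reporting how many patients per arm contribute and their baseline severity.

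The cost is a short text change, modest extra programming and longer run time. SAP section 2 already uses sequential imputation for the clinical outcomes, so the approach is familiar to the team. Imputing every month within every diary category (12 × 4 = 48 variables for 110 patients per arm) is not needed and could be unstable for rare items such as surgery.

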This study will be a pragmatic randomized trial comparing strategies for managing patients with a new episode of LBP and sciatica in primary care. One strategy is usual care (UC) directed within primary care during the initial 4 weeks. The other strategy is early physical therapy (EPT) with patients receiving 6-8 sessions in the initial 4 weeks. We will examine patient-centered outcomes and subsequent healthcare utilization [and costs] over a 1-year follow-up period. Based on our hypothesis that the first few weeks provide an opportunity to positively influence the clinical course of LBP with sciatica, the difference between strategies occurs in the 4 weeks after an initial primary care encounter. The study will use a pragmatic approach comparing these strategies under realistic clinical circumstances. Recruitment will occur from primary care clinics in the University of Utah Health Care system. [name] has previously led successful clinical trials in this system. Patients visiting a primary care clinic with a chief complaint of LBP and sciatica will be potentially eligible. Eligible patients who provide informed consent will undergo baseline assessment followed by randomization to a treatment group (UC / EPT). Both groups will receive first-line medication as needed and advice and education emphasizing remaining active and the inappropriateness of early imaging or specialist referral as recommended by the APS/ACP guideline.³³ The UC group will be managed within primary care for the next 4 weeks with a stepped approach (ie, referral for additional care considered after 4 weeks if symptoms do not improve). The EPT group will be referred to physical therapy for 6-8 sessions in the first 4 weeks based on current best evidence supporting a centralizing approach. Follow-up evaluations will occur 4 weeks, 6 months and 1 year after enrollment.

C.3 Subjects

We will recruit 220 patients with LBP and sciatica making initial entry into the healthcare system in primary care. Initial entry is defined as not having treatment from any provider for LBP or sciatica in the past 6 months. Potential candidates must satisfy all inclusion criteria:

- I. Symptoms of pain and/or numbness between the 12th rib and buttocks, which, in the opinion of the primary care provider, are originating from tissues of the lumbar region.

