Numeric Pain Rating Scale (NPRS): 0-10 NPRS ('0' = no pain, '10' = worst imaginable pain) will be used to assess pain intensity. We will use separate NPRS ratings of low back and leg pain. NPRS have excellent test-retest reliability.⁸⁴ Our prior research has found the NPRS responsive to change, with an MCID of 2 points among patients with acute LBP receiving physical therapy.⁸⁸ A 2-point MCID is also reported for patients with LBP and sciatica.⁸⁶ [*NPRS will be a secondary outcome and explored as a moderator.*]

EuroQol (EQ-5D): A generic quality of life instrument⁹¹ will be used to assess health outcomes on a scale that may be referenced to other disease conditions.⁹² The EQ-5D covers 5 domains: mobility, self-care, usual activities, pain/discomfort, and anxiety/depression. Each domain has 3 response categories: "no problems"; "some problems"; or "inability or extreme problems." Responses are combined to 5-digit health state classification. The EQ-5D yields a total of 243 possible health states. Valuation of each health state is available.⁹³ The EQ-5D is reliable and responsive to change in patients with LBP^{94,95} and is commonly used in economic evaluation of interventions for LBP.

Fear Avoidance Beliefs Questionnaire (FABQ): assesses patients' beliefs about how physical activity and work may affect their LBP and perceived risk for re-injury.⁹⁸ The FABQ has two subscales; a 7-item work subscale (FABQW), and 4-item physical activity subscale (FABQPA). Test-retest reliability of the subscales is high.^{98,99} Validity is supported by associations with concurrent and future disability and work loss in patients with acute and chronic LBP.¹⁰⁰⁻¹⁰³ [*FABQ will be explored as a potential moderator.*]

Pain Catastrophizing Scale (PCS): a 13-item scale assessing the extent to which people catastrophize in response to pain.¹⁰⁶ Each item is scored from 0-4. The PCS is reported as a total score, and is composed of three sub-scales: rumination, magnification, and helplessness. Pain catastrophizing plays an important role in the transition from acute to chronic LBP.¹⁰² [*PCS will be explored as a potential moderator.*]

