Follow-up examinations will be conducted 4 weeks, 6 months, and 1 year after baseline. The 4-week examination permits evaluation of the immediate effects of early physical therapy. 6-month and 1-year examinations evaluate intermediate and long-term effects of treatment received during the first 4 weeks. The 4-week follow-up will be conducted in-person by a blinded research assistant in order to re-assess the physical examination. 6-month and 1-year follow-ups will be conducted online by e-mailed links using REDCap. In addition to the self-reports described previously, follow-up assessments will also collect:

Satisfaction: Patient satisfaction with care for LBP will be measured at the 4-week follow-up using a 10-item instrument that has been validated and found capable of distinguishing different dimensions of satisfaction (caring, information and treatment effectiveness) among patients with LBP attending primary care.¹¹¹

Global Rating of Change: will be completed at each follow-up using a 15-point scale¹¹² that asks the patient to rate the degree of change in his or her condition from enrollment to the present..

C.6 Procedures for Treatment (see Appendix C for copies of treatment forms)

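### The 1-year cost-effectiveness analysis appears to set 12 months of costs against the score at the 1-year visit, leaving EQ-5D at 4 weeks and 6 months without direct weight

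*Protocol*

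**What the plan says.** Protocol C.9, Specific Aim #2, plans two cost-effectiveness analyses. The short-term one takes direct and indirect costs for the first 4 weeks, and for the effect it states: "The effectiveness of these costs will be based on OSW and EQ-5D scores at 4 weeks". The long-term one has a single defining sentence: "Long-term CE analysis will use cost and effect data measured at 1-year". That sentence names no instrument; the use of OSW and EQ-5D at 1 year is inferred from the short-term rule. The next sentence reads: "Costs and effects will be measured in the same year; eliminating the need for inflation adjustment or discounts".

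On the inputs, Protocol C.5 says of costs: "We will collect cost and utilization data monthly via REDCap". Follow-up visits are at 4 weeks, 6 months and 1 year. Of the EQ-5D, C.5 says: "Valuation of each health state is available". It does not link that valuation to the cost-effectiveness analysis.

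The protocol text mentions no QALY, area under the curve or interpolation between visits. The available SAP text contains no cost analysis. Part of the SAP was not available, so its silence is given no weight.

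**The concern.** A cost accumulated over a year and a score taken on one day at the end of it do not cover the same period. The 4-week analysis has the same form, but its window is short. Over 12 months the gap matters more, and the 6-month visit would enter neither cost-effectiveness analysis.

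The design makes this more than a formality. Protocol C.2 says that "the difference between strategies occurs in the 4 weeks after an initial primary care encounter", and C.5 says that "6-month and 1-year examinations evaluate intermediate and long-term effects of treatment received during the first 4 weeks". A benefit that appears early and then shrinks is therefore one plausible pattern. The cost of the added physical therapy falls early and sits inside the 12-month total; the health gained early would not be counted against it. A benefit that appears late would be credited as if it had lasted all year. The incremental ratio, the net benefit and the acceptability curve would all carry that choice.

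**Working it through.** **The plan's own figures.** The documents give no figure for the cost-effectiveness analysis. The nearest are the OSW power figures in C.11 (difference 7, SD 16, two-sided 0.05):

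- 6 months, 90% of 110 = 99 per group: SE = 16 × √(2/99) = 2.274; 7/2.274 = 3.078; power = Φ(3.078 − 1.960) = 86.8% (stated: at least 86%).
- 1 year, 80% of 110 = 88 per group: SE = 16 × √(2/88) = 2.412; 7/2.412 = 2.902; power = Φ(2.902 − 1.960) = 82.7% (stated: at least 82%).

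Both reproduce. The concern does not depend on them, but the second is used under the objection.

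**Weight of each visit.** The visit times in C.5 are 0, 4/52 = 0.0769, 0.5 and 1 year. The trapezoid weights are:

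| Visit | Formula | Area weight | Weight if the 1-year score is used |
|---|---|---|---|
| Baseline | 0.0769/2 | 0.0385 | 0 |
| 4 weeks | (0.5 − 0)/2 | 0.2500 | 0 |
| 6 months | (1 − 0.0769)/2 | 0.4615 | 0 |
| 1 year | (1 − 0.5)/2 | 0.2500 | 1 |

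The two middle visits carry 0.2500 + 0.4615 = 0.7115, or 71%.

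**When the two measures agree.** Let d4, d6 and d12 be the between-group EQ-5D differences at 4 weeks, 6 months and 1 year, with no baseline difference. Setting d12 = 0.25·d4 + 0.4615·d6 + 0.25·d12 gives d12 = 0.333·d4 + 0.615·d6. For a benefit, a smaller d12 falls short of the area and a larger one exceeds it.

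**Illustration (assumed trajectory).** Suppose the difference changes in a straight line from 4 weeks to 1 year and a fraction f of d4 remains at 1 year. Six months lies (0.5 − 0.0769)/(1 − 0.0769) = 0.4583 of the way along, so d6 = d4 × [1 − 0.4583(1 − f)].

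| f | Area/d4 | 1-year score as % of area |
|---|---|---|
| 0 | 0.500 | 0% |
| 0.25 | 0.615 | 41% |
| 0.5 | 0.731 | 68% |
| 0.75 | 0.846 | 89% |
| 1 | 0.962 | 104% |
| 1.5 | 1.192 | 126% |

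With an assumed d4 of 0.05 and f = 0.5, the area is 0.05 × 0.731 = 0.037 QALY and the 1-year difference is 0.025. The ratio divides by the effect, so for the same cost difference it would be 1/0.684 = 1.46 times as large if the score were treated as a year's gain.

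**Data available for an area measure.** Apply the C.11 OSW follow-up rates (90% at 6 months, 80% at 1 year) to EQ-5D. The 1-year score is then available for 0.80 × 220 = 176 patients. Both later visits are available for 176 if losses are nested, 0.90 × 0.80 × 220 = 158 if independent, and (0.90 + 0.80 − 1) × 220 = 154 if disjoint. Loss at 4 weeks is not given and would lower these counts.

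**The case against.** **A rule does exist on the natural reading.** A reader might infer that the 1-year effect is undefined whichever way the sentence is taken. The text does not support that. If the sentence means the score at 1 year, that score is the rule, and Aim 1 separately describes a baseline-adjusted model for EQ-5D change to 1 year, although the cost-effectiveness text does not refer to it. Only on the other reading, effects over the year, is a rule missing. That reading is possible: one phrase governs both costs and effects, and diary costs cannot be measured at a single point. The parallel with the short-term rule makes it less likely but does not rule it out.

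**The percentages are not a bias estimate.** A reader might take them as the error in the planned result. The protocol never calls the 1-year score a QALY, and cost per EQ-5D point at 1 year is a different quantity from cost per QALY. The percentages describe error only if the score is read as a year's health gain. This objection stands.

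**Fading is not the documented expectation.** The 1-year power reproduces with the same 7-point OSW difference as at 6 months, and C.11 calls its effect estimates realistic. The Specific Aims speak of preventing persistent pain and disability. Suppose the EQ-5D effect were likewise equal at 6 months and 1 year, with a 4-week effect k times as large (k assumed). The 1-year difference is then 1/(0.25k + 0.7115) of the area: 120%, 104%, 92% and 83% for k = 0.5, 1, 1.5 and 2. That 7 points is a detectable difference on another instrument, so it does not establish the EQ-5D pattern. It does show that the 0% and 41% cases require most of the effect to vanish.

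**Early effects are reported elsewhere.** This is true: they appear in the short-term analysis and in the Aim 1 comparisons. Neither sets them against 12-month costs.

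**Conclusion.** The point holds as a low-severity improvement. On its most natural reading, the long-term sentence compares 12 months of costs with a score at one visit and gives no direct weight to visits that would carry 71% of an area measure. Earlier values could still enter indirectly through imputation, hence no direct weight rather than none. On the alternative reading, the rule for combining visits is missing.

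The size cannot be determined from the documents, which give no EQ-5D effect at any visit. Under assumed trajectories it runs from almost nothing (104% for a constant effect; 83% to 120% when the 6-month and 1-year effects are equal) to large when the effect fades (68% if half remains, 0% if none does). The direction depends on the trajectory. The figures assume equal baselines and linear change between visits.

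It should not be inferred that the trial's main conclusion is at risk. This concerns one effect definition within a secondary aim; the 6-month OSW comparison and the sample size do not depend on it.

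**What to change.** For the 1-year analysis, define the EQ-5D effect as baseline-adjusted QALYs: the trapezoid area under the EQ-5D index at 0, 4 weeks, 6 months and 12 months, compared between randomized groups with baseline EQ-5D as a covariate, using the multiple imputation already planned. Report cost per OSW point at 1 year as a separate result, described as an endpoint score set against 12-month costs.

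The cost is plan wording and analysis code. No new data are needed: EQ-5D is collected at every visit, and the imputation model in SAP section 2 already includes the EQ-5D index. There are two downsides. The area assumes linear change between visits, including the long gaps from 4 weeks to 6 months and from 6 months to 1 year. It also needs every visit, so reliance on imputation rises: 154 to 176 of 220 patients would have both later visits, against 176 with the 1-year score, before any 4-week loss.
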